2 BACKGROUND AND RATIONALE

The increasing prevalence of liver disease in the UK, the resulting increase in morbidity and mortality, and the regional variation in survival has been extensively reviewed in reports of the Lancet Commission on Liver Disease in the UK and the Atlas of Variation in Risk Factors for Liver Disease in England (1,2). Below we summarise these reports as well as evidence from an extended review of the literature that was carried out to support this application. This review highlighted serious questions about the current provision and delivery of care for patients with CLD, especially in patients who were admitted to hospital as an emergency.

Mortality rates from CLD in the UK have increased 400% since 1970, and in people younger than 65 years have risen almost five-fold (1,2). Most patients die in working age and CLD is now the third biggest cause of premature mortality. In 2018, liver disease was the leading cause of death for those age 35-49 years. However, the prevalence of liver disease and its outcome is not uniform across the UK. Studies in England have shown wide variation: premature mortality varies 7.7-fold and hospital admissions 8.5-fold by Clinical Commissioning Group (CCG). This variation is closely linked to the level of socio-economic deprivation. People with CLD who live in the most deprived areas of England die nearly 10 years earlier and have a mortality rate that is twice as high compared to those who live in the most affluent ones (1,2).

CLD has a wide range of different aetiologies. People with CLD, particularly if it is alcohol-related, often first come to medical attention with an unplanned emergency admission (EA) to hospital when their disease is already advanced. Over a quarter of these patients die within 60 days of their first EA (3,4). Re-admissions are common and associated with a worse prognosis, and nearly 70% of patients who survive a first EA will die within 5 years (3).

Provision of specialist care for people with CLD admitted as emergencies shows wide variation across the UK with major imbalances between service provision and local disease burden (5). A study of CLD patients admitted to hospital between 2004 and 2012 in England and Wales suggested that early input

King's College Hospital MHS

NHS Foundation Trust

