3 OBJECTIVES

3.1 Primary Objective

The overall aim is to identify which characteristics of treatments and services for acutely ill people with CLD impact on care processes and outcomes.

The project will investigate:

1. Time trends in acute secondary care use for patients with CLD and their outcomes.

2. Regional variation in acute secondary care use for patients with CLD and their outcomes.

3. The impact of regional clinical networks on referral and transfer patterns.

4. The impact of regional, hospital and patient characteristics on critical care use of CLD patients who had a first EA.

5. The impact of regional, hospital and patient characteristics on use of liver transplantation after a first emergency hospital admission in patients with CLD.

6. The impact of coordinated specialist outpatient review after discharge on readmissions, referral for transplantation, and mortality.

Our analyses will also seek to assess the impact of the Covid-19 pandemic on all these aspects of care.

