Other relevant hospital trust-level characteristics to be included from NHS England datasets will be the relevant hospital size in beds, bed occupancy and transplant centre status.

Time period considerations

Up-to-date organisational characteristics of bed numbers, occupancy and transplant status will be available throughout the study period but characteristics from some data sources will need to be updated through direct contact with NHS hospital trusts.

Work Package 2: Understanding Determinants of Variation in Practice and Outcomes after Emergency Hospital Admission.

The study will use linked existing electronic patient-level healthcare data to map the full "patient journey" of patients with CLD. The patient journey will start from the first emergency hospital admission and we will examine determinants of Intensive Care Unit (ICU) admission, length of stay, inter-hospital transfer for specialist care or liver transplantation and in-hospital and longer term mortality.

We will use three existing national datasets linked at patient-level:

- Hospital Episodes Statistics (HES) data (inpatient, outpatient data, A&E attendances and ONS mortality data)
- Intensive Care National Audit and Research Centre Case Mix Programme (ICNARC-CMP) database
- UK Transplant Registry maintained by NHS Blood and Transplant

The research team analysing the data will not have access to patient identifiers. Please see the Data Flow Diagram attached as appendix 2.

We will include all adult patients with CLD disease who were admitted with a first emergency hospital admission in the study period from 1 April 2009 to 31 March 2022 according to HES-APC data, with an expected cohort size of about 100,000 CLD patients. Patients will be considered to have CLD according to ICD-10 diagnostic codes.

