2. Regional variation in acute secondary care for patients with chronic liver disease and its outcomes:

First, we will estimate the rate of EAs for CLD per 100 000 people per year in 44 regions. The numerator will be the number of CLD patients with a first EA and the denominator populations will be derived by aggregating the updated 2011 Census results for patients of 18 years and older in each region. We will use multilevel Poisson regression models to produce empirical Bayes estimates for regional EA rates without and with adjustment for patient and regional characteristics. We will analyse regional differences in critical care use during the EA, total length of hospital stay, readmission rate and total time spent in hospital within the first year, the rate of liver transplantation, and in-hospital and 1-year mortality. Multilevel regression models will be used to quantify the regional variation and to produce empirical Bayes estimates for each region. We will assess the impact of the Covid-19 pandemic on regional variation in EA rates and outcomes.

3. Impact of regional clinical networks on referral patterns: The development of regional networks, shaped as hub-and-spoke models, will be explored by observing referral patterns after a first EA of patients with CLD. We will create "super-spells" for each patient and identify within this super-spell the hospital of the EA and the hospital trust where most of the care was provided. These results will be used to identify the hub (a hospital that typically receives referrals) and the spokes (hospitals that typically refer patients) in each clinical network. The configuration and characteristics of these networks (e.g., in terms of regional coverage, number and characteristics of referred patients, type of

care provided predominantly in the hub and spokes, changes to referrals pre- and post- Covid-19)) will be compared.

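### Question 3 identifies referrals from the admitting hospital and the main-care trust alone, so transfers where the receiver gives the smaller share of care, and intermediate centres, go uncounted

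*Protocol*

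**What the plan says.** Objective 3 in Protocol section 3.1 is "The impact of regional clinical networks on referral and transfer patterns". Section 4 (Work Package 2) also lists "inter-hospital transfer for specialist care or liver transplantation and in-hospital and longer term mortality" among the events whose determinants will be examined.

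Section 9, question 3 says network development "will be explored by observing referral patterns after a first EA of patients with CLD". It builds a super-spell for each patient and takes two facts from it; the analysts will "identify within this super-spell the hospital of the EA and the hospital trust where most of the care was provided". The next sentence gives their purpose: "These results will be used to identify the hub (a hospital that typically receives referrals) and the spokes (hospitals that typically refer patients"). Networks are then compared, among other things, "in terms of regional coverage, number and characteristics of referred patients, type of" care given in hub and spokes, and on "changes to referrals pre- and post- Covid-19".

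Section 9 names no provider sequence, transfer event or transfer date. It gives no metric for the main-care trust (days, episodes or critical care days). The same question in section 4 offers no other derivation. Separately, section 4, Work Package 1, item 5 describes a national audit in which trusts are already classified by network role, with regional centres and transplantation centres as distinct categories.

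**The concern.** A referral is a movement: one provider sends, another receives. The two facts named describe where the patient came in and where most care was given. They show a sender and a receiver only if they differ, and they differ only if the receiver's share of care outweighs the sender's. That is narrower than the protocol's own idea of a hub, which rests on receiving referrals and not on giving most of the care.

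Two stated outputs depend on it. The number and characteristics of referred patients would describe transfers with long receiving stays. The pre/post-Covid comparison would move whenever hub stays shorten, waits for transfer lengthen or repatriation becomes more common, even if referral behaviour were unchanged.

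The pair also sets a hospital against a hospital trust, so a move between two sites of one trust has no defined status.

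**Working it through.** The plan states no referral rate, sample size or stay length for question 3, so there is no figure to reproduce. The check has three steps.

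**Step 1: example records.** Read most of the care as most days (an assumption, since no metric is given).

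| Record | Receiver's share of days | Seen as a referral? |
|---|---|---|
| 12 days local, 3 at hub, 5 back local | 3/20 = 15% | No |
| 6 days local, then death on hub day 2 | 2/8 = 25% | No |
| 2 days local, 14 at hub | 14/16 = 87.5% | Yes |
| 1 day local, then death on hub day 3 | 3/4 = 75% | Yes |
| Short local stay, 3 days at a regional centre, 20 at a transplant centre | Transplant centre has the most | Yes, but the regional centre is not seen |

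A short or fatal transfer is therefore lost only when the receiver's share is the smaller one.

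**Step 2: possible size (all inputs assumed).** Let A be days before transfer, H days at the hub, and R days after repatriation (probability p, otherwise 0). A true transfer is captured if H > A + R.

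*Exponential stays, mean 7 days after repatriation.* Captured share = H/(H + A) × [(1 − p) + p × H/(H + 7)], with A and H now the means.

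- Best case, A = 3, H = 14, p = 0: 14/17 = 82% captured, 18% missed.
- Worst case, A = 5, H = 3, p = 0.5: 0.375 × (0.5 + 0.5 × 0.3) = 0.375 × 0.65 = 24% captured, 76% missed.

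*Log-normal stays, log-SD 0.9, median 5 days after repatriation.* With p = 0, the missed share is Φ[ln(A/H)/(0.9√2)], with A and H now the medians. Values for p > 0 are simulated.

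| Median A, H | Missed, p = 0 | p = 0.25 | p = 0.5 |
|---|---|---|---|
| 2, 14 | 6% | 13% | 19% |
| 4, 8 | 29% | 37% | 45% |
| 7, 5 | 60% | 66% | 71% |

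Across both sets the missed share runs from about 6% to 76%.

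**Step 3: spurious change with true referrals held constant.**

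- Exponential, p = 0.25, means moving from A = 5, H = 14 to A = 7, H = 10. Before: 14/19 × (0.75 + 0.25 × 14/21) = 0.737 × 0.917 = 67.5%. After: 10/17 × (0.75 + 0.25 × 10/17) = 0.588 × 0.897 = 52.8%. The ratio is 0.78, an apparent fall of about 22%.
- Log-normal, median A = 4, p = 0.25, median hub stay shortened from 8 to 6 days: captured share goes from 63% to about 54%, an apparent fall of about 13%.
- Log-normal, median A = 4, H = 8: repatriation of 10% gives about 68% captured and 50% gives about 55%, so two hubs with equal true referrals look different.

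**The case against.** The strongest objection is that the rule is inferred. Section 9 never writes that a referral exists only if the two sites differ, it calls itself an overview, and section 4 promises explicit coding schemes. The referral counts and the Covid comparison appear in a list of examples with no counting rule. This stands in part: the comparison is a reading. But the two facts are the only ones named, their use is stated, and no other section gives a different route from super-spell to referral. The point concerns a derivation the protocol fixes, not detail it leaves out.

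A reader might infer that hubs and spokes themselves would be mislabelled. The documents do not support that. A hub is a hospital that typically receives referrals, which is an aggregate label. On assumed volumes, a hub with 200 true inbound transfers at 30% to 75% capture still shows 60 to 150, against 5 for a spoke. The audit classification in section 4 offers an independent check.

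A reader might also infer that every short, fatal or repatriated transfer is lost, or that referred patients must look less ill than they are. Step 1 refutes the first. The background section says "Over a quarter of these patients die within 60 days of their first EA", which makes short fatal stays plausible but does not settle a direction. Suppose 25% of transferred patients die at the hub, with log-normal stays as above and no repatriation. If fatal cases have medians of 4 days local and 3 at the hub (others 4 and 8), capture is 41% against 71%, and mortality among captured referrals is 0.25 × 0.41/(0.25 × 0.41 + 0.75 × 0.71) = 16%. If fatal cases move early, with medians of 1 and 3 days, capture is 81% and the same formula gives 28%. The direction depends on the assumption.

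Finally, question 3 is descriptive, and the hospital/trust mix may be loose wording. Both are fair and limit the weight of the point.

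**Conclusion.** The point holds in a limited form. As written, question 3 sees a referral only through the admitting hospital and the main-care trust. It therefore does not count transfers in which the receiver gives the smaller share of care, and it drops intermediate centres in a chain. Referral counts and the characteristics of referred patients are tilted towards long receiving stays, and the pre/post-Covid comparison is mixed with length of stay, delay before transfer and repatriation. Hub and spoke labels are less affected.

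This rests on the natural reading of the two-fact derivation. The numbers rest further on measuring care in days and on assumed stays and repatriation rates. The range of about 6% to 76% missed, and the spurious falls of 13% and 22%, show that the effect could matter; they do not estimate it. The documents fix neither its size nor its case-mix direction. The derivation should be changed because it does not match the stated objective on referral and transfer patterns.

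**What to change.** In section 9, question 3:

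- Derive referrals from the ordered sequence of providers within each super-spell, with the trust as the single unit at both ends.
- Count each onward move to a trust not yet visited in that super-spell as a directed sender-to-receiver referral, whatever the stay or outcome there.
- Classify a move back to an earlier trust separately as a repatriation. Counting every change of trust would turn returns into hub-to-spoke referrals and distort the counts that define the hubs.
- Use the directed referrals for the number and characteristics of referred patients and for the pre/post-Covid comparison.
- Keep the trust giving most of the care as a separate descriptor, with its metric stated.
- Check the derived hubs and spokes against the audit classification in section 4, Work Package 1, item 5.

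The cost is a short text edit and a small change to the derivation code. Provider by episode should already be needed to build super-spells and assign the main-care trust, so no new data are required. Brief transfers will also be counted; reporting referrals by length of stay at the receiver shows their contribution. A step-down to a trust not previously visited would still count as onward, and the check against the audit classification would help to reveal it.

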1 INTRODUCTION

Liver disease is a serious and increasing health problem in the UK. However, people with liver disease often do not know that they are affected until they need to be admitted to hospital as an emergency. These people are often very ill, and a quarter of them die within two months of coming into hospital. The care they get when they are in hospital, and after being discharged, varies greatly across the country. This variation in care has major effects on how long they survive. Survival of those who live in the most deprived areas is half that of those who live in the most well-off ones. We want to understand how and why the place where people live and the care that is available to them affect the way they are treated and their survival. We also want to see how variation in outpatient care after discharge makes a difference. Through this research we hope to understand what clinical practices have the best results and how we can guarantee that they are delivered across the country.

To do this research, we will gather very detailed information about the arrangements for care given to people with liver disease in each hospital in England and then use the health information routinely recorded when people are treated in these hospitals. Information from different parts of the NHS will be 'linked' together into a single database so we can analyse the complete course of people's illness. Data analysed by the research team will have names and all other identifying information removed. We will analyse data from more than 100,000 people with liver disease who had emergency admissions to NHS hospitals in England over more than a decade.

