4. Impact of regional, hospital and patient characteristics on critical care use of chronic liver disease patients who had a first emergency admission: We will explore the association between which of the regional characteristics (e.g., network arrangements, prevalence of CLD, use of transplantation), hospital characteristics (e.g., transplant centre status, specialist staffing, ICU capacity, ICU case-mix), and patient characteristics (e.g., type of CLD and comorbidity, age, sex, socioeconomic deprivation) are associated with the proportion of cases admitted to critical care, their clinical condition at critical care admission, the duration of critical care, and the proportion of cases for whom critical care was withdrawn. We will also explore changes in critical care use as a result of the Covid-19 pandemic. Multilevel logistic regression models will be used to estimate adjusted odd ratios that capture the impact of the regional, hospital and patient characteristics and the Covid-19 pandemic on critical care use.

5. Critical care use and clinical outcomes after a first EA in patients with CLD: We will characterise hospitals according to the proportion of patients that are admitted to critical care and whether they were admitted to critical care early or late in order to explore to what extent hospitals with more frequent and earlier critical care admissions of CLD patients after an EA have better short-term outcomes (in-hospital mortality and readmissions, total time spent in hospital and mortality during the year following the EA). The results will be analysed using multilevel logistic regression including the level and timing of critical care use as hospital-level characteristics with adjustment for key patient characteristics, including age, sex, socioeconomic deprivation, and comorbidity.

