6. Use of liver transplantation after a first EA in patients with CLD: Using the linked UK Transplant Registry data, we will explore the regional variation in the use of liver transplantation in the first year after a first EA. We will use multilevel logistic regression models to explore to what extent the regional variation is associated with specific patient and health service characteristics , and whether patterns of transplantation changed in response to the Covid-19 pandemic. We will use Cox regression with sequential stratification to estimate the impact of liver transplantation on survival. Sequential stratification is a relatively new method which has wide applicability to observational studies where the time to an event (e.g., death) is of interest and the treatment being compared (i.e., liver transplant) is time dependent.

7. Impact of coordinated specialist outpatient review after discharge on readmissions, referral for transplantation, and mortality: We will compare the outcomes of patients who are discharged alive from hospital after their first EA from hospitals that offer coordinated specialist outpatient review with patients from hospitals where this type of outpatient review is not available. We will use multilevel Cox regression to estimate differences in time to readmission, referral for transplantation, and death.

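### Questions 1, 2 and 5 have no fixed-window mortality endpoint shorter than one year; the only earlier one is in-hospital death, whose window depends on discharge and transfer practice

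*Protocol*

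**What the plan says.** Protocol section 9 names the mortality outcomes question by question.

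- **Questions 1 and 2** (time trends, regional variation) end their outcome lists with "the rate of liver transplantation, and in-hospital and 1-year mortality". Section 4 gives the same pair for question 1.
- **Question 5** (critical care use and outcome) asks whether hospitals with more frequent and earlier critical care "have better short-term outcomes (in-hospital mortality and readmissions, total time spent in hospital and mortality during the year following the EA"). The model is a multilevel logistic regression, with level and timing of critical care as hospital-level characteristics.
- **Section 4, Work Package 2 overview**, lists "inter-hospital transfer for specialist care or liver transplantation and in-hospital and longer term mortality".
- **Question 7** uses "multilevel Cox regression to estimate differences in time to readmission, referral for transplantation, and death", but only in patients discharged alive.

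No 30-, 60- or 90-day mortality counted from admission is named anywhere.

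Two other statements bear on the point. The linked data include "Hospital Episodes Statistics (HES) data (inpatient, outpatient data, A&E attendances and ONS mortality data"). On early risk, section 2 says "Over a quarter of these patients die within 60 days of their first EA", and section 1 says "a quarter of them die within two months of coming into hospital".

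Transfers are joined into super-spells, used to "identify within this super-spell the hospital of the EA and the hospital trust where most of the care was provided". That step is described under question 3 only.

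**The concern.** In-hospital death has an observation window that the hospital partly sets. A patient discharged on day 10 who dies on day 20 counts as a survivor. The same patient kept in until day 20 counts as a death. If transfers are not joined, a patient moved to a hub also leaves the first hospital's count.

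The protocol itself treats what sets this window as variable. Length of stay is an outcome by year and by region, inter-hospital transfer is under study, and referral patterns are compared before and after Covid-19. A difference in in-hospital mortality between hospitals, regions or years can therefore reflect when patients leave as well as whether they survive.

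Question 5 is the most exposed, because hospitals are the units compared and critical care use may itself be linked to length of stay and transfer. One-year mortality avoids the discharge problem, but it mixes the early deaths that critical care might prevent with deaths many months later. If the in-hospital result points one way and the one-year result is flat, the planned mortality outcomes cannot tell an early benefit that was later diluted from a discharge artefact.

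**Working it through.** The plan gives no figure of its own on this point, so there is none to reproduce. The first step compares the endpoints; the others are illustrations.

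**1. Mortality endpoints and their windows**

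| Question | Endpoint | Window ends |
|---|---|---|
| 1, 2, 5 | In-hospital death | At discharge; at transfer too, unless spells are joined |
| 1, 2, 5 | One-year mortality | Fixed, one year |
| 7 | Time to death | Discharged-alive patients only |

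In questions 1, 2 and 5, every horizon under one year is therefore the in-hospital one.

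**2. Same 60-day survival, different in-hospital mortality**

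Inputs: 60-day mortality of 25% in both hospitals (sections 1 and 2); share of those deaths that occur before discharge, *s* (assumed; not in the documents).

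In-hospital mortality = 0.25 × *s*; odds = p / (1 − p).

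- *s* = 75% vs 65%: 0.1875 vs 0.1625; odds 0.2308 vs 0.1940; OR 1.19.
- *s* = 80% vs 60%: 0.20 vs 0.15; odds 0.2500 vs 0.1765; OR 1.42.

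On 60-day mortality the OR is 1.00 in both cases, by construction.

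**3. Length of stay alone**

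Assume a constant hazard that gives 25% dead at 60 days: h = −ln(0.75)/60 = 0.00479 per day. Take assumed stays of 10 and 14 days.

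- Dead by day 10: 1 − exp(−10h) = 4.7%.
- Dead by day 14: 1 − exp(−14h) = 6.5%.
- OR for the 10-day against the 14-day hospital: 0.71, with the same survival curve.

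**4. How much of one-year mortality is early**

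Section 2 says nearly 70% of those who survive a first EA die within 5 years. Assume a constant hazard for this group, applied from day 60: −ln(0.30)/5 = 0.241 per year. Day 60 to one year is 305/365 = 0.836 years, so the risk among day-60 survivors is 1 − exp(−0.241 × 0.836) = 18.2%. As a share of the cohort this is 0.75 × 18.2% = 13.7%.

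- One-year mortality = 25% + 13.7% = 38.7%; early share = 25/38.7 = 65%.
- If that hazard is doubled: 0.75 × 33.1% = 24.8%; early share = 25/49.8 = 50%.

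On these assumptions, one third to one half of one-year deaths fall after day 60.

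**5. What the later deaths do to an early effect**

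Suppose 60-day mortality falls by a fifth, from 25% to 20%, and later risk is unchanged at 18.2%. A fifth is the size section 2 reports for early specialist input, borrowed here only as a scale.

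- At 60 days: OR = (0.20/0.80)/(0.25/0.75) = 0.75.
- At one year: 20% + 0.80 × 18.2% = 34.6% vs 38.7%; OR = (0.346/0.654)/(0.387/0.613) = 0.84.

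The one-year endpoint still shows the effect, but attenuated.

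**The case against.** Several objections have force.

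- **One-year mortality is also labelled short-term.** A reader might infer that in-hospital death is the only short-term mortality endpoint. Question 5 does not support that: it puts one-year mortality under the same label, so a fixed-window endpoint independent of discharge already sits beside in-hospital death. What stands is narrower: nothing fixed is shorter than a year.
- **Sixty days is not an adopted window.** A reader might infer that the protocol contradicts its own 60-day risk window. It does not. The figure is a background citation, and no objective or endpoint uses it. It is a documented candidate, and another early window could be justified.
- **The outcomes are reported together.** Length of stay or total time in hospital, and one-year mortality, appear alongside in-hospital death, and no endpoint is ranked primary. This helps a careful reader. It does not recover deaths soon after discharge.
- **One-year mortality contains every 60-day death.** True, and on the assumptions above half to two thirds of it is early. It is less specific, not uninformative.
- **The two-hospital illustration is not a bias estimate for question 5.** Correct. It has no critical care exposure. Variation in discharge practice unrelated to critical care use adds between-hospital noise, not bias.
- **Super-spells may deal with transfer.** They may, but the protocol describes them only for question 3. It does not say whether question 5 counts deaths over them, or to which hospital a death is attributed. They would not capture deaths after discharge home.
- **Section 9 is an overview, and a separate analysis plan could add a window.** It could. The pairing of in-hospital with one-year mortality is nevertheless what the protocol states, repeatedly, and a better measure is available from the same data.

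**Conclusion.** The point holds in limited form. In questions 1, 2 and 5 the only mortality endpoint shorter than one year depends on when and how patients leave hospital. Groups with the same early survival can therefore differ on it.

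The ORs of 1.19 and 1.42 show that modest differences in discharge practice can produce apparent effects of a relevant size. They rest on assumed in-hospital shares and are not estimates for these hospitals. It would go too far to say that the planned question 5 result is biased. That requires discharge or transfer practice to be associated with critical care use, which is plausible but not shown in the documents.

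The conclusion also assumes that the ONS mortality data carry dates. The protocol does not say so in words, but one-year mortality and time to death both need them.

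**What to change.** In question 5, and for consistency in questions 1 and 2, add all-cause mortality within a fixed window from the EA admission date, for example the 60 days cited in the background. Derive it from the linked ONS mortality data, irrespective of place of death, and name it the main early-mortality measure. Keep one-year mortality as planned and report in-hospital mortality descriptively.

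The cost is a wording change and one extra derived outcome. No new linkage or follow-up is needed, because the planned one-year endpoint already requires longer follow-up than an early window.
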